6.3.3. Clinical Asthma Exacerbations

6.3.3.1. Variable Definition

A clinical asthma exacerbation (CAE) is defined as a clinically judged deterioration in asthma control, as determined by the investigator and as evidenced by new or worsening asthma signs or symptoms based on the patient history, asthma control diary, physical examination, and/or ambulatory or clinic visit assessment of lung function AND that results in a medical intervention, including at least 1 of the following:

- use of systemic corticosteroids (injection, or if oral, at least a doubling from the current OCS dose for at least 3 days)
- asthma-specific hospital admission
- asthma-specific emergency department visit

Additional medication and/or medical intervention that would satisfy the CAE definition occurring within 7 days of the last day of a prior CAE event will be considered as part of the same event for analysis purposes.

The CAE start and stop dates will be collected in order to determine the exacerbation duration. The start date of a CAE will be the start date of the initial medical intervention (eg, use of systemic corticosteroids [injection, or if oral at least a doubling from the current OCS dose for at least 3 days], asthma-specific hospital admission, or asthma-specific emergency department visit, whichever comes first). The stop date is the last day of systemic corticosteroids (injectable), or for those with a doubling of the OCS dose, the stop date is when the return to their baseline dose (dose prior to exacerbation), or the last day of an asthma-specific hospitalization or emergency department visit, whichever is later. For patients receiving at least a doubling from their current dose of OCS for at least 3 days that did not return to baseline (dose prior to exacerbation), the CAE stop date will be the day that they have been on a new stable dose for at least 10 days.

6.3.3.2. Analysis

The annualized rate of CAEs will be analyzed using the generalized linear model (GLM) for data from the negative binomial distributions, commonly referred to as the negative binomial (NB) regression model. The NB model will include factors for treatment group, randomization strata (age and OCS dose as defined in Section 2.4), number of exacerbations in the previous year, and an offset variable. The offset variable will be calculated as the logarithm of follow-up duration minus the summed duration of exacerbations during the follow-up. Age and OCS dose will be based on data recorded in the clinical database.

The ratio of CAE rate between the treatment groups and its 95% CI will be estimated from the NB model. Treatment effect will be evaluated using the likelihood based chi-square test. The analysis of clinical asthma exacerbations will be on-treatment, excluding exacerbations observed after stopping study treatment. For patients who complete treatment, the treatment period will be defined from the first dose of study drug to the end of treatment (week 24) visit. For patients who prematurely discontinue treatment, the treatment period will be defined from the first dose of study drug to the last dose of study drug + 4 weeks. Analyses will only be performed if a sufficient number of patients have exacerbations for the model to converge satisfactorily.

The following sample SAS[®] code pertains to the analysis of CAEs.

```
proc genmod data=<<>>;
  class treatment strata1 strata2;
  model cae=treatment strata1 strata2 nexac /dist=negbin link=log offset=log_futime;
  estimate "CAE rate ratio" treatment 1 -1;
  lsmeans treatment /diff exp cl;
  ods output lsmeans=<<>>;
  ods output lsmeandiffs=<<>>;
run;
```

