4.5.1. Discontinuation of Study Treatment

If premature discontinuation of study treatment occurs for any reason, the patient should continue attending remaining study visits while off study treatment. The patient will continue to receive study provided OCS (prednisone) treatment for the remainder of their participation in the study. The patient should not be considered withdrawn from the study due to interruption or discontinuation of study treatment. For this study, it is very important to continue collecting data from all patients whether or not they complete treatment.

If premature discontinuation of study treatment occurs, the patient should return to the clinic as soon as possible for a study treatment discontinuation visit. All evaluations should be performed as specified in the protocol for the early withdrawal visit (see Table 5). The investigator must determine the reason for and the date of discontinuation of study treatment and record this information in both the source documentation and the Study Drug Treatment Completion CRF. The patient's continued participation in the study must be discussed by the investigator and site staff with the patient; the investigator and site staff must also request the patient to continue attending study visits according to the study visit schedule with all assessments completed up to week 24 (visit 19). The OCS dose and safety assessments at week 24 (visit 19) are the priority assessments for patients that prematurely discontinue study treatment. At a minimum, the investigator should make every effort to obtain information regarding serious adverse events, OCS dose, and survival status at week 24. A safety follow-up visit (visit 20) should be conducted 8 weeks after visit 19.

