9.5.2. Secondary Endpoints

The secondary efficacy endpoints for this study are the following:

- Proportion of patients achieving $\geq 50\%$ reduction in OCS dose at weeks 20 to 24 relative to the OCS dose at DoR/baseline, while maintaining asthma control
- Proportion of patients achieving dose reduction to ≤ 5 mg daily dose at weeks 20 to 24, while maintaining asthma control
- Percent change from DoR/baseline in OCS dose at weeks 20 to 24
- Proportion of patients achieving less than 5 mg decrement in OCS dose (ie, the minimal and non-responders) compared with the OCS dose at DoR/baseline at weeks 20 to 24, while maintaining asthma control
- Clinical asthma exacerbation-related:
 - Annualized rate of CAEs requiring a burst of systemic corticosteroid (injection, or if oral, at least a doubling from the current OCS dose for at least 3 days); an asthma-specific hospital admission; or an asthma-specific emergency department visit during the treatment period (weeks 0 to 24)
- Proportion of patients discontinuing OCS at weeks 20 to 24, while maintaining asthma control

The order of the secondary endpoints above is the order of hierarchy to be used for controlling type I error as described in Section [9.6](#).

[figure not shown]
9.5.3. Other Secondary Efficacy Endpoints:

Other efficacy endpoints for this study are the following:

- Time to first CAE
- Other clinic lung functions including the following:
 - Pre-bronchodilator FEV₁: change from DoR/baseline to weeks 4, 8, 12, 16, 20, and 24 or early withdrawal
 - Post-bronchodilator FEV₁: change from DoR/baseline to weeks 4, 12, 20, and 24 or early withdrawal
- Ambulatory lung function: change in AM and PM PEF from run-in baseline at each week through week 24 or early withdrawal
- AQLQ + 12 score: change from DoR/baseline to weeks 4, 8, 12, 16, 20, and 24 or early withdrawal
- ACQ-6: change from DoR/baseline to weeks 4, 8, 12, 16, 20, and 24 or early withdrawal
- Change in total inhalations of reliever bronchodilator medication (eg, SABA) (number of inhalations per 24 hours: day+night) from run-in baseline at each week through week 24 or early withdrawal
- Number of nighttime awakenings due to asthma over the 24-week treatment period
- Change in total asthma symptom scores from run-in baseline at each week through week 24 or early withdrawal
- EQ-5D score: change from DoR/baseline to week 24 or early withdrawal
- SGRQ score: change from DoR/baseline to weeks 12 and 24 or early withdrawal

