3. POPULATIONS/ANALYSIS SETS

3.1. Intent to Treat Analysis Set

The intent to treat (ITT) analysis set will include all randomized patients. In this population, treatment will be based on the treatment to which patients were randomized, regardless of which treatment they actually received.

Two analytic approaches are planned using the ITT analysis set.

- In the first approach, all data collected from patients will be included, regardless of continued adherence to their assigned study treatment.
- In the second approach, data collected from patients during the treatment period will be included, up to the point at which patients discontinue from their assigned study treatment (on-treatment). For patients who completed treatment in this study, the treatment period will be defined from the first dose of study drug to the end of treatment (week 24) visit. For patients who prematurely discontinue treatment, the treatment period will be defined from the first dose of study drug to the last dose of study drug + 4 weeks.

For all efficacy endpoints, the on-treatment approach will be utilized as the main approach to analysis. However, it should be noted that all patients will be included in the analysis of the primary and secondary endpoints related to OCS dose reduction by incorporating missing data (due to dropout) as nonresponders. The analytic approach including all data collected from patients will additionally be conducted as sensitivity analyses for the primary endpoint.

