4.3. Multiple Comparisons and Multiplicity

A fixed sequence multiple testing procedure will be implemented to test the primary and secondary variables while controlling the overall type I error rate at 0.05. If the resulting

two-sided p-value from the primary comparison is ≤ 0.05 , then the next comparison of interest (first secondary variable) will be interpreted inferentially at 0.05. This process continues through the secondary variables until either all comparisons of interest are interpreted inferentially, or until the point at which the resulting two-sided p-value for a comparison of interest is > 0.05 . At the point where $p > 0.05$, no further comparisons will be interpreted inferentially. The hierarchy of endpoints is as defined in Section 6.3.1.

No multiplicity adjustments will be made for other efficacy and exploratory analyses.

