6.3.1. Secondary Variables

The secondary efficacy endpoints for this study are as follows:

- Proportion of patients achieving $\geq 50\%$ reduction in OCS dose at weeks 20 to 24 relative to the OCS dose at the date of randomization (DoR)/baseline, while maintaining asthma control

- Proportion of patients achieving dose reduction to ≤ 5 mg daily dose at weeks 20 to 24, while maintaining asthma control
- Percent change from DoR/baseline in OCS dose at weeks 20 to 24
- Proportion of patients achieving less than 5 mg decrement in OCS dose (ie, the minimal and non-responders) at weeks 20 to 24 compared with the OCS dose at DoR/baseline, while maintaining asthma control
- Annualized rate of clinical asthma exacerbations requiring a burst of systemic corticosteroid (injection, or if oral, at least a doubling from the current OCS dose for at least 3 days); an asthma-specific hospital admission; or an asthma-specific emergency department visit during the treatment period (weeks 0 to 24)
- Proportion of patients discontinuing OCS at weeks 20 to 24, while maintaining asthma control

Testing of the secondary variables will be performed using the sequential testing procedure in the order specified above, as described in Section 4.3.

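### The alpha-controlled exacerbation rate is analysed only on treatment, and no all-data analysis to week 24 is committed to beside it

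*SAP*

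**What the plan says.** SAP 6.3.1 lists the endpoint fifth of six, as "Annualized rate of clinical asthma exacerbations requiring a burst of systemic corticosteroid" and so on, and adds: "Testing of the secondary variables will be performed using the sequential testing procedure in the order specified above, as described in Section 4.3". SAP 4.3 sets that procedure up to "test the primary and secondary variables while controlling the overall type I error rate at 0.05", with two-sided p-values.

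Protocol 9.5.2 gives the period for the endpoint; its definition ends "asthma-specific emergency department visit during the treatment period (weeks 0 to 24". Protocol 9.5.6 uses the ITT set for efficacy. Protocol 9.5.6.3 specifies a negative binomial model whose offset is the log of follow-up duration less days in exacerbation. Neither section restricts events to time on study drug.

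SAP 6.3.3.2 does: "The analysis of clinical asthma exacerbations will be on-treatment, excluding exacerbations observed after stopping study treatment". For early stoppers the window closes at last dose plus 4 weeks. The offset still refers to follow-up duration and is not tied to that window.

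Protocol 4.5.1 asks patients who stop study drug to attend the remaining visits to week 24, and says: "For this study, it is very important to continue collecting data from all patients whether or not they complete treatment". The procedures table (Protocol 3.16, Table 5) has CAEs assessed at every treatment-period visit.

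On analyses that use those later data, SAP 3.1 says: "The analytic approach including all data collected from patients will additionally be conducted as sensitivity analyses for the primary endpoint". SAP 4.5 and 6.3 say that similar analyses may be done for selected variables. They do not name the variables, and the surrounding text concerns measures summarised by visit.

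**The concern.** Stopping study drug may be related to asthma control. Protocol 7.1.8 classes withdrawal for worsening asthma or a CAE as lack of effect, and SAP 5.2 plans Kaplan-Meier plots to look for differential dropout. If patients who stop go on to have a different exacerbation rate, a window that closes at last dose plus 4 weeks estimates a different quantity from the weeks 0 to 24 rate in the protocol.

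Other endpoints in the sequence have some protection. The primary and the categorical OCS endpoints place early stoppers in the lowest category. Percent change in OCS dose has a Wilcoxon sensitivity analysis that gives early withdrawers the worst rank (SAP 6.3.2.2.3). The CAE rate has no committed counterpart, and time to first CAE (SAP 6.4.2.2) is also on treatment only. A claim of fewer exacerbations could therefore rest on one handling of discontinuation, with any alternative chosen after the results are known.

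**Working it through.** **The plan's own figures.** The documents give no CAE rate, dispersion, dropout rate or power for this endpoint, so there is no stated CAE figure to reproduce. The only sample size is for the primary endpoint: 76 per group, odds ratio 2.63, 90% power. The proportional-odds formula n = 6(1.960 + 1.282)² / [ln(2.63)² × (1 − Σp̄³)], with Σp̄³ about 0.098, gives 74.7, so 75 per group, and 90.5% power at 76. That agrees with the plan, and nothing below changes it.

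**Effect of the window on the rate ratio.** All inputs here are assumptions:
- on-treatment rates of 1.6 per year on placebo and 1.0 on reslizumab, ratio 1.0/1.6 = 0.625;
- for those who stop, the on-treatment window ends at day 84 of 168, so half the period is dropped;
- after that, the placebo rate is multiplied by m = 1.5 or 2.5, and the reslizumab rate by 1.5m (2.25 or 3.75).

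For an arm with on-treatment rate λ, stopping proportion d and off-treatment multiplier k, the all-data rate to week 24 is λ[1 + 0.5d(k − 1)].

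| Stopping, reslizumab / placebo | m = 1.5 | m = 2.5 |
|---|---|---|
| 10% / 10% | 1.0625/1.640 = 0.648 | 1.1375/1.720 = 0.661 |
| 15% / 5% | 1.0938/1.620 = 0.675 | 1.2063/1.660 = 0.727 |
| 5% / 15% | 1.0313/1.660 = 0.621 | 1.0688/1.780 = 0.600 |

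The all-data ratio exceeds the on-treatment ratio when d(k − 1) is larger on reslizumab, and falls below it when d(k − 1) is larger on placebo. The direction is therefore not fixed.

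**Simulation.** The assumptions were 76 per arm, placebo 2.0 CAEs per year, on-treatment ratio 0.60, dispersion 0.8, off-treatment rate 1.5 times placebo in both arms, and 1500 runs.
- 10% stopping per arm: mean ratio 0.60 on treatment and 0.63 all-data; power 54% and 49%.
- 20% stopping on reslizumab, 10% on placebo: 0.59 and 0.67; power 54% and 39%.
- No drug effect: rejection of 4% to 6% for both analyses.

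Stopping was drawn independently of each patient's underlying rate. The null result therefore shows no inflation under these assumptions, and does not test stopping driven by the patient's own risk.

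**Offset.** If on-treatment counts were divided by full follow-up, the ratio would shift for a mechanical reason. With an assumed ratio of 0.70, 20% stopping on reslizumab and 10% on placebo, and half the period lost, it becomes 0.70 × (1 − 0.10)/(1 − 0.05) = 0.663.

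**The case against.** The case on the other side is substantial, and much of it stands.

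- **On-treatment is a legitimate choice.** Agreed. SAP 3.1 makes it the main approach for all efficacy endpoints and keeps the ITT set; only the time window differs.
- **CAEs are not singled out.** Correct. Percent change in OCS dose is also modelled on observed on-treatment data, and only its Wilcoxon sensitivity analysis penalises withdrawal.
- **All-data analyses are already allowed.** They are permitted in SAP 4.5 and 6.3, so a reader should not infer that the SAP rules one out for CAEs. Permission for unnamed variables is still not a commitment. The corticosteroid-burden analyses in SAP 6.3.2.2.3 cover steroid days and cumulative dose and do not give a CAE rate.
- **The restriction is recorded.** A reader might infer a concealed change from the protocol. The documents do not support that: Protocol 9 leaves changes and detail to the SAP, Table 14 shows the on-treatment text labelled as a clarification, and the SAP introduction says discrepancies will be explained in the study report. What remains is that Table 13, the list of changes from the protocol, omits it.
- **Few important events may be lost.** Events within 4 weeks of the last dose are kept. Apart from pregnancy, Protocol 3.14 sets no formal rules for stopping study drug, and a second steroid burst does not itself end treatment (Protocol 3.1.4.1). The frequency of stopping for worsening asthma is not stated.
- **Later CAE data may be incomplete.** Protocol 4.5.1 gives priority to OCS dose and safety, and its minimum data set does not include CAEs. This bears on how the added analysis should define exposure.
- **Limited reach.** The primary and four secondary endpoints must succeed before this one is tested.

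**Conclusion.** The point holds as a gap in prespecification. An endpoint in the confirmatory sequence, defined by the protocol over weeks 0 to 24, has only an on-treatment analysis committed to, although patients who stop are asked for data to week 24 and the primary endpoint has a committed all-data analysis.

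The size cannot be derived from the documents. Under the assumed rates, 0.625 moves to about 0.65 to 0.66 with equal 10% stopping, to 0.68 to 0.73 with 15% on reslizumab and 5% on placebo, and to 0.60 to 0.62 with those reversed. A reader might infer that the on-treatment analysis flatters reslizumab or inflates the false-positive rate. Neither is established. If more placebo patients stop because of worsening asthma, the on-treatment ratio can be the less favourable one, and the simulation showed no inflation under its assumptions. The issue is which effect is estimated and whether the result is robust to that choice. This is a cheap improvement that leaves the main analysis as it is.

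**What to change.** Add to SAP 6.3.3.2 one named supportive analysis: a negative binomial model of all observed CAEs to week 24 in all randomised patients, with the same factors and covariate as the main model. Base its offset on the time over which CAEs were actually ascertained, ending at the last CAE assessment for patients who supply only the minimum data after stopping. Report it beside the on-treatment result and outside the testing sequence.

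State that the main model's offset uses on-treatment time, so that events and exposure share one window. List the on-treatment restriction in Table 13 with its rationale.

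The cost is one extra model and a few lines of text. Sample size, alpha and the hierarchy do not change. The drawback is that CAE ascertainment after discontinuation may be incomplete, so the report should give the number of early stoppers in each arm and how long each was followed for CAEs.

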6.4. Other (and Exploratory) Efficacy Variable(s) and Analysis

As described previously in Section 4.5, an on-treatment approach will be adopted as the primary analysis for the efficacy variables assessed by-visit. In this analysis, the treatment period will be defined from the first dose of study drug to the end of treatment (week 24) visit for patients who completed treatment and from the first dose of study drug to the last dose of study drug (+4 weeks) for patients who discontinued treatment early. Measurements collected outside of these defined timeframes will be excluded from the analyses and endpoint will be defined within these timeframes. All results will be included in the patient listings. For selected key variables, additional sensitivity analyses may also be performed in which all post-baseline measurements collected during the study will be included and endpoint will be defined within this extended timeframe.

6.4.1. Other (and Exploratory) Efficacy Variable(s)

The other (and exploratory) efficacy endpoints are:

- Time to first clinical asthma exacerbation
- Other clinic lung functions including the following:
 - Pre-bronchodilator FEV₁: change from DoR/baseline to weeks 4, 8, 12, 16, 20, 24 or early withdrawal; [REDACTED]
 - Post-bronchodilator FEV₁: change from DoR/baseline to weeks 4, 12, 20, 24 or early withdrawal; [REDACTED]
- Ambulatory lung function: change in morning (AM) and evening (PM) peak expiratory flow (PEF) from run-in baseline at each week through week 24 or early withdrawal

- Asthma Quality of Life (AQLQ) + 12 score: change from DoR/baseline to weeks 4, 8, 12, 16, 20, and 24 or early withdrawal
- ACQ-6 score: change from DoR/baseline to weeks 4, 8, 12, 16, 20, 24 or early withdrawal; [REDACTED]
- Change in total inhalations of reliever bronchodilator medication (number of inhalations per 24 hours: day+night) from run-in baseline at each week through week 24 or early withdrawal
- Number of nighttime awakenings due to asthma over the 24-week treatment period
- Change in total asthma symptom score from run-in baseline at each week through week 24 or early withdrawal
- European Quality of Life 5-dimension health state utility index (EQ-5D) score: change from DoR/baseline to week 24 or early withdrawal
- St. George's Respiratory Questionnaire (SGRQ) score: change from DoR/baseline to weeks 12 and 24 or early withdrawal
- [REDACTED]

6.4.2. Time to First Clinical Asthma Exacerbation

6.4.2.1. Variable Definition

Refer to Section 6.3.3.1 for the definition of a clinical asthma exacerbation.

6.4.2.2. Analysis

The Kaplan-Meier (KM) method will be used to estimate and compare the distributions of time to first CAE between treatment groups. Time to first event will be analysed for on-treatment events.

The time period for the on-treatment analysis will extend from the date of first dose of study drug to the cessation of study treatment, defined as the date of the end of treatment (week 24) visit for patients who completed treatment and the date of last dose (+4 weeks) for patients who discontinued treatment early. Patients without an event during this time frame will be censored at either the date of the end of treatment (week 24) visit for patients who completed treatment or at the date of last dose (+4 weeks) for patients who discontinued early.

The hazard ratio (95% CI) and p-value will be estimated using a Cox proportional hazards regression model adjusting for the stratification factors.

The following sample SAS[®] code pertains to the analysis of time to first CAE.

```
proc lifetest data=<<>> outsurv=<<>>;
  time tcae*censor(0);
  strata treatment;
  ods output quartiles=<<>>;
run;
```

```
proc phreg data=<<>>;
  class treatment (ref='PBO');
  model ttcae*censor(0) = treatment / rl ties=discrete;
  strata strata1 strata 2;
  ods output parameterestimates=<<>>;
  ods output globaltests=<<>>;
run;
```

A KM plot will be provided for the time to first CAE by treatment group.

